4.3.4 Protocol Deviations

Protocol deviations identified during site monitoring will be captured in a protocol deviation log and categorized as major or minor deviations. The major protocol deviations will be summarized by treatment groups. Listings will be generated for the major and minor protocol deviations.

4.3.5 Study Drug Exposure and Study Drug Compliance

A summary table of study drug exposure and compliance will be provided. Number of weeks on study treatment (BIIB104 or placebo), will be calculated as (date of last dose – date of first dose +1) /7. The cumulative duration of weeks on study treatment will be displayed (≥ 1 , ≥ 2 , ≥ 4 , ≥ 6 , ≥ 8 , ≥ 12 weeks). Descriptive statistics will be presented for days on study treatment.

Compliance, which is the percentage of study treatment taken up to the last dose, calculated as (the actual number of dose taken / by the number of doses a subject is expected to take until the date of last dose) *100, will be summarized both as a continuous variable and a categorical variable (i.e., < 80, 80 to < 90, 90 to ≤ 100 , and $> 100\%$).

Time on study (in weeks) will be summarized both as a continuous variable and a categorical variable. The categorical variable will be grouped as ≤ 2 , $2 - \leq 4$, $4 - \leq 6$, $6 - \leq 8$, $8 - \leq 10$, $10 - \leq 12$, and > 12 weeks.

A listing of study drug administration records for placebo subjects who received any dose of active treatment will be provided.

4.4 Efficacy Analysis

4.4.1 General Considerations

For efficacy endpoints, the following treatment groups of BIIB104 (per randomization) will be evaluated and compared with placebo:

- High dose (0.5 mg BID)
- Low dose (0.15 mg BID)

All efficacy analyses will be performed on the ITT population. In addition, the per-protocol population will also be used in the analyses of primary and key secondary efficacy endpoints including MCCB Working Memory, MCCB Neurocognitive Composite, UPSA-Bi, SCoRS.

Primary analysis for continuous endpoints

The primary analysis is the mean difference of the change from baseline to Week 12 between treatment and control group in the ITT population. Data will be censored when a subject prematurely discontinues the study treatment. The estimate of this analysis reflects the treatment effect of BIIB104 if the drug were taken as directed. This is considered [de jure] efficacy estimand [ICH E9 (R1) Addendum 2014, 2017].

The change from baseline will be summarized by treatment group at each post-baseline visit. A mixed model repeated measures (MMRM) model will be used as the primary analysis to analyze change from baseline of the endpoint of interest, using fixed effects of treatment group, study visit, study visit-by-treatment interaction, baseline value of the endpoint, and baseline-by-visit interaction. Region (stratification factor for randomization) will be included as a fixed effect but may be omitted in the case that the model fails to converge. An unstructured covariance matrix will be used to model the within-patient variance-covariance errors. If the unstructured covariance matrix results in a lack of convergence, the following structures will be used in order: heterogeneous Toeplitz (TOEPH), heterogeneous compound symmetry (CSH), antedependence (ANTE1), heterogeneous autoregressive (ARH1), autoregressive (AR1) and compound symmetry (CS). The first covariance structure yielding convergence will be used. If a structured covariance is used, the empirical “sandwich” estimator of the standard error (SE) of the fixed effects parameters will be used to deal with possible model misspecification of the covariance matrix. The Kenward-Roger approximation will be used to estimate the denominator degrees of freedom. The primary treatment comparison is BIIB104 treatment group versus placebo at the end of Week 12. In the primary analysis, missing data are assumed to be missing at random (MAR) [Rubin 1976]. To account for the interim analysis at the time of the final analysis, the median unbiased estimate of the primary treatment effect will be calculated as a supporting analysis.

However, for UPSA-Bi and SCoRS, which only have assessments at baseline and at Week 12, the primary analysis will be based on subjects who have both baseline and Week 12 assessments. An analysis of covariance (ANCOVA) model will be applied adjusting for treatment group and baseline value of the endpoint (UPSA-Bi or SCoRS, respectively).

Sensitivity analysis: Reference-based multiple imputation approach

The following sensitivity analysis will be performed to assess the robustness of the primary analysis with respect to deviation from the MAR assumption. All sensitivity analyses will be conducted for the ITT population.

Intermittent (non-monotonic) missing data will be imputed based on the MAR assumption and with a multiple imputation model using Markov chain Monte Carlo (MCMC) method within each treatment group. The imputation models will include baseline value and the values at each post-baseline week for the endpoint of interest. The MCMC method in the PROC MI procedure in SAS will be used with a single chain, with a burn-in of 1000, and a thinning of 100 and non-informative priors for all parameters.

Reference-based multiple imputation (MI) approach will be used to impute missingness post treatment discontinuation and consider a missing not at random (MNAR) mechanism for monotonic missing data. Imputed values in the reference group (placebo) will assume MAR. Imputed values in the BIIB104 treatment groups will be based on data from the placebo group using sequential regression MI model. Each sequential regression model (i.e., for imputation of values at a given week) will include visits of endpoint. This approach assumes no sustained benefit of BIIB104 after discontinuation of study treatment and limits post-discontinuation effects to that of placebo.

Two hundred imputations will be performed and from each of the imputed datasets, least square (LS) mean differences from placebo and their standard errors will be combined using Rubin's method [Rubin 1987]. PROC MIANALYZE procedure is used to produce a pooled LS mean estimate of treatment difference at Week 12, its 95% CI, and a pooled p-value.

Complementary Analysis: include data after intercurrent events

This is a complementary analysis to the primary and sensitivity analyses (efficacy estimand) for the ITT population. All observed data including those collected after intercurrent events [ICH E9 (R1) Addendum 2017], i.e. premature discontinuation of the study treatment, will be included. The estimate of this analysis reflects the treatment effect of BIIB104 seen as actually taken. This is considered [*de facto*] effectiveness estimand. When all data after intercurrent events are included, the same MMRM model as the primary analysis will be applied. In this complementary analysis, missing data are assumed to be missing at random [Rubin 1976].

The per-protocol analysis will be done using the same model as the primary analysis and applying in the per-protocol population.

Responder Analysis: threshold determined using distribution-based method

This is a supplementary analysis to assess the effect of individual treatment response in the ITT population only. The threshold, defined as the minimal clinically important difference (MCID), will be estimated based on the distribution-based approach and will use 1/2 pooled standard deviation at baseline calculated from subjects in the ITT population. A subject will be classified as a responder if their change from baseline (in terms of improvement) is greater or equal to the threshold, otherwise they will be classified as a non-responder. All subjects with missing data at Week 12 will be classified as non-responders.

The number of responders and non-responders will be modelled using a logistic regression with treatment group and baseline included as covariates. Region will also be included but may be omitted in the case the model fails to converge.

Visit windows for mapping efficacy endpoints

For efficacy data that are summarized by visit, data collected on all scheduled visits and all unscheduled visits will be mapped to an appropriate analysis visit using the windowing scheme shown in the following few tables. If there are 2 or more assessments available in the same analysis window for a subject, the assessment closest to the target visit day will be used for analysis. If there are 2 or more assessments in the same analysis window with the same distance from the target visit day, the later assessment will be used.

Table 2: Visit Windows for Efficacy Endpoints: MCCB, [REDACTED], and PANSS

Analysis visit	Target visit day	Analysis visit window
Baseline	1	Prior to the time of, or within one day after, the first treatment dose
Week 2	15	[2, 28]
Week 6	43	[29, 70]
Week 12	85	[71, 91]

* If subject terminate the treatment before Day 71, their visits will be mapped to corresponding analysis visit based on the analysis day (ADY).

Table 3: Visit Windows for efficacy endpoints: UPSA-Bi, SCoRS, [REDACTED]

Analysis visit	Target visit day	Analysis visit window
Baseline	1	Prior to the time of, or within one day after, the first treatment dose
Week 12	85	[71, 91]
Early Termination	N/A	[2, 70]

* If subject terminate the treatment early before Day 71, their visits will be mapped to nominal visit of “early termination”.

Table 4: Visit Windows for Efficacy Endpoints: CGI-S/CGI-I

Analysis visit	Target visit day	Analysis visit window
Baseline	1	Prior to the time of, or within one day after, the first treatment dose
Week 6	43	[2, 70]
Week 12	85	[71, 91]

* CGI-I does not have baseline collected and therefore its visits are applied to Week 6 and 12.

* If subject terminate the treatment early before Day 71, their visits will be mapped to corresponding analysis visit based on the analysis day (ADY).

Considerations for multiple comparison adjustments

There will be no multiple comparison adjustments for primary, secondary efficacy [REDACTED] endpoints, nor the subgroup analyses.

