8.2. Exclusion Criteria

Candidates will be excluded from study entry if any of the following exclusion criteria exist at Screening, or at the timepoint specified in the individual criterion as listed:

1. Individuals who are investigational site staff members directly involved in the conduct of the study and their family members, site staff members otherwise supervised by the Investigator, or Sponsor employees directly involved in the conduct of the study.
2. Participation in other studies involving treatment with an investigational drug within 30 days or 5 half-lives (whichever is longer) prior to randomization and/or during study participation.
3. Participation in a trial that uses any component or version of the MCCB or the UCSD Performance-Based Skills Assessment test within the previous 6 months.
4. Participation in cognitive remediation therapy within 6 months prior to randomization.
5. Participation in ongoing cognitive behavioral therapy that was initiated <8 weeks prior to Baseline/Day 1.
6. Screening MCCB Working Memory Domain T-score ≥ 60 .
7. Current DSM-5 diagnosis of schizoaffective disorder on the MINI 7.0.2 for Psychotic Disorders.
8. Current DSM-5 diagnosis of major depressive episode, manic and hypomanic episode, panic disorder, agoraphobia, social anxiety disorder, obsessive-compulsive disorder, post-traumatic stress disorder, and/or generalized anxiety disorder on the MINI 7.0.2 for Psychotic Disorders.
9. Lifetime DSM-5 diagnosis of antisocial personality disorder, anorexia nervosa, bulimia nervosa, and/or binge-eating disorder on the MINI 7.0.2 for Psychotic Disorders.
10. Meets the DSM-5 diagnosis of moderate or severe substance use disorder (excluding nicotine dependence) within 12 months of screening on the MINI 7.0.2 for Psychotic Disorders interview.
11. DSM-5 diagnosis of Intellectual Disability (intellectual developmental disorder).
12. Other severe, acute, or chronic medical or psychiatric condition or laboratory abnormality that may increase the risk associated with study participation or investigational product administration or that may interfere with the interpretation of study results and, in the judgment of the Investigator, would make the subject inappropriate for entry into this study.
13. Pregnant or breastfeeding female subjects; male subjects with partners who are currently pregnant.

CONFIDENTIAL

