16.1.2.1. Analysis of the Primary Endpoint

The primary endpoint is the change of MCCB Working Memory Domain score from baseline to Week 12. An MMRM model will be used as the primary analysis to analyze change from baseline in Working Memory Domain score using fixed effects of treatment, visit, treatment by visit interaction, baseline Working Memory Domain score, baseline Working Memory Domain score by visit interaction, and region.

[figure not shown]
In the analysis of the primary endpoint, missing data will be assumed to be missing at random (MAR). An unstructured variance-covariance structure will be used to model the within patient measurements variability. If this analysis fails to converge, other structures will be tested such as heterogeneous autoregressive, heterogeneous compound symmetry, or heterogeneous Toeplitz. The variance-covariance structure that results in the smallest Akaike information criterion will be used. The Kenward-Roger approximation will be used to estimate the denominator degrees of freedom. Sensitivity analyses will be carried out to assess the robustness of primary analysis to deviation from the MAR assumption. Details of sensitivity analyses and assumptions for different missing patterns will be described in the SAP.

CONFIDENTIAL

The information contained herein may not be used, disclosed, or published without the written consent of
Biogen MA Inc.

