16.6. Sample Size Considerations

Fifty-one subjects per treatment group will have approximately 80% power to detect a true mean difference of 3.5 in change from baseline MCCB Working Memory Domain score to Week 12 between the treatment and placebo groups. With the assumed drop-out rate of 30%, 73 subjects are required from each group to maintain the 80% power. This power calculation is based on a 2-sided *t*-test assuming equal variance with a final significance level of 0.1, and an SD of 7. The statistical software EAST 6.3® is used for sample size calculation. The sample size may be re-estimated based on blinded data review and evolving development of this study.

CONFIDENTIAL

The information contained herein may not be used, disclosed, or published without the written consent of
Biogen MA Inc.

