4. STATISTICAL ANALYSIS METHODS

4.1 General Considerations

This statistical analysis plan (SAP) describes the planned analyses for this phase 2 study evaluating the primary, secondary [REDACTED] objectives. This SAP also covers the planned interim and final analyses, and therefore there is no separate SAP for the interim analysis.

Data listings will be provided by treatment group, visit, and subject, if applicable. Summary statistics and statistical analyses will only be presented for data where detailed in this SAP. For continuous data, summary statistics will include the arithmetic mean, arithmetic standard deviation (SD), median, minimum (Min), maximum (Max) and n; for log-normal data the geometric mean and geometric coefficient of variation (CV) will also be presented. For categorical data, frequency count and percentages will be presented. Data listings will be provided for all subjects up to the point of withdrawal, with any subjects excluded from the relevant population highlighted. Summary statistics and statistical analyses will generally only be performed for subjects included in the relevant analysis population.

Data will be summarized and presented by treatment group, defined in Table 1. Data will be listed by treatment group. Exposure to study medication will be tabulated by treatment group.

Unless stated otherwise, baseline data are defined as the data collected prior to the time and/or on the day of the first dose, which is usually the same day as the Day1/Baseline visit. If data are not available on Day 1 for safety assessment, the measurements recorded up to 3 days prior to first dose (i.e. Day -3) will be used as baseline. For efficacy assessments, the Day1/Baseline visit may be performed over 2 days, i.e., on Day 1 and Day 2. Therefore, an assessment performed on the second day of visit Day1/Baseline (i.e., Day 2), will be used as baseline if not already performed on the first day of visit Day1/Baseline (i.e., Day 1). If there is more than one value on/before the day of the first dose, the non-missing value closest to and prior to the first dose will be used as the baseline value

Unless stated otherwise, all statistical tests will be 2-sided with statistical significance level of 0.10.

The statistical software, SAS 9.4®, will be used for all summaries and statistical analyses.

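### The Screening MCCB Working Memory score, already collected before randomization, is left out of the primary model, which gives up some precision at almost no cost

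*SAP*

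**What the plan says.** Protocol Section 5 schedules the MCCB at Screening Visit 1 (Table 3, Day -35 to Day -8) and again at Day 1, Week 2, Week 6 and Week 12 (Table 4). SCI-PANSS and CGI-S are also taken at both Screening and Day 1. UPSA-Bi and SCoRS are not listed at Screening.

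Protocol 8.2, criterion 6, excludes subjects on the "Screening MCCB Working Memory Domain T-score" (60 or more), so a Screening score should exist for every eligible subject.

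SAP 4.1 reduces several pre-dose readings to one: "the non-missing value closest to and prior to the first dose will be used as the baseline value". The same section lets an efficacy baseline be taken on the second day of the Day 1 visit, and SAP Table 2 accepts an MCCB baseline up to one day after the first dose.

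The SAP 4.4.1 primary MMRM is fitted "using fixed effects of treatment group, study visit, study visit-by-treatment interaction, baseline value of the endpoint, and baseline-by-visit interaction", with region added. Protocol 16.1.2.1 has the same terms, ending in "baseline Working Memory Domain score by visit interaction, and region". Neither names the Screening score. The imputation model for intermittent missing data in SAP 4.4.1 lists only baseline and post-baseline values.

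**The concern.** Working Memory is a performance test, so one reading reflects both the subject's level and occasion-to-occasion error. Adjusting for a single reading leaves part of that error in the Week 12 residual variance. A second reading taken before randomization can remove some of it. Treatment cannot affect that reading, so adjusting for it does not bias the contrast. A practice gain from Screening to Day 1 and the entry cut-off at 60 are common to all arms.

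The stake is precision. The design aims at about 80% power at two-sided alpha 0.10 with 30% dropout. SAP 5 takes the interim LS mean differences and standard errors from the primary model, so precision also bears on the futility decision.

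**Working it through.** **Inputs from Protocol 16.6.** Test: "This power calculation is based on a 2-sided" t-test, "assuming equal variance with a final significance level of 0.1, and an SD of 7". Target: "Fifty-one subjects per treatment group will have approximately 80% power to detect a true mean difference of 3.5". Dropout: "With the assumed drop-out rate of 30%, 73 subjects are required from each group to maintain the 80% power". The documents do not say whether SD 7 refers to raw change or to the residual after baseline adjustment. They give no T-score SD and no correlation between occasions; every correlation below is an assumption.

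**1. The plan's own figure.** Two-sample t-test (noncentral t), difference 3.5, SD 7, two-sided alpha 0.10: n = 50 per arm gives power 0.799 and n = 51 gives 0.806. Then 51/0.70 = 72.9, rounded up to 73, and 3 x 73 = 219. The figures reproduce.

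**2. Formula for the gain.** Let s, b, w be the scores at Screening, Day 1 and Week 12. The Week 12 residual variance with s and b as covariates, divided by that with b alone, is

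ratio = 1 - p^2, where p = (r_sw - r_sb x r_bw) / sqrt[(1 - r_sb^2)(1 - r_bw^2)].

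Using change from Day 1 as the response does not alter this, because b is in both models. With equal correlation r the ratio simplifies to (1 + 2r)/(1 + r)^2.

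**3. Equal correlations.** Taking 7 as the planned model's residual SD and spending one extra degree of freedom:

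| r | ratio | power at 51 per arm | n per arm for 80% |
|---|---|---|---|
| 0.5 | 0.889 | 84.5% | 45 |
| 0.6 | 0.859 | 85.5% | 44 |
| 0.7 | 0.830 | 86.6% | 42 |
| 0.8 | 0.802 | 87.6% | 41 |
| 0.9 | 0.776 | 88.5% | 40 |

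The variance reduction is 11-22%.

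**4. Correlations that decay with time.** First family: test reliability 0.7-0.9, true-score correlation over 12 weeks 0.8-0.9, Screening 3 weeks before Day 1. Ratios run from 0.895 to 0.965 and power from 84.3% to 81.8%.

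Second family, with r_bw held at 0.755:

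| r_sw | r_sb | ratio | power at 51 per arm |
|---|---|---|---|
| 0.72 | 0.78 | 0.898 | 84.2% |
| 0.70 | 0.78 | 0.927 | 83.1% |
| 0.68 | 0.78 | 0.951 | 82.3% |
| 0.70 | 0.85 | 0.972 | 81.6% |
| 0.65 | 0.78 | 0.978 | 81.4% |

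Worked example, last row: numerator 0.65 - 0.78 x 0.755 = 0.0611; p = 0.149; ratio 1 - 0.022 = 0.978. Over both families the reduction is about 2-10%. With reliability 1 and pure first-order autoregressive decay, r_sw = r_sb x r_bw, so p = 0 and there is no gain.

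**5. Checks.** An information calculation for the MMRM with 73 per arm and 30% monotone dropout gives ratios of 0.825-0.875 (equal correlations 0.8 to 0.6) and 0.91-0.95 (three decay cases). A simulated ANCOVA with Screening scores of 60 or more excluded (assumed mean 40, SD 10, equal correlations) moves power from 80.6% to 85.0% at r = 0.6, from 80.2% to 85.8% at 0.7 and from 80.1% to 86.6% at 0.8. The entry cut-off does not remove the gain.

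**6. If SD 7 is the SD of raw change.** With equal variances, r = 1 - 49/(2 SD^2). An assumed T-score SD of 9-12 gives r = 0.70-0.83. The planned model's residual variance, SD^2(1 - r^2), is then 41.6-44.8 rather than 49. The 51 per arm already act like 51 x 49/44.8 = 56 to 51 x 49/41.6 = 60, with power of about 84-86% before the Screening score is used.

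**The case against.** The strongest reply is that nothing here needs correcting. The MMRM with one baseline is valid and pre-specified, the sample size reproduces, and one covariate rather than two is a choice. That stands: a reader might infer that the primary analysis is biased or the trial underpowered, and the documents support neither.

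The size is also uncertain. Decay is plausible because Screening may precede Day 1 by up to 35 days, and exclusion 3 makes it the first MCCB within a trial for at least six months. The gain may then be one or two points of power. This stands, and it is why only the range should be quoted. It is also tempting to divide 51 by the variance ratio and report an effective sample size. But 51 comes from an unadjusted t-test; if SD 7 is the SD of raw change, the planned model already does better than that (step 6), so the starting point would be wrong.

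Two further inferences go too far. One is that the Screening score serves only as an entry filter: the SAP 4.1 rule and the Table 2 window could let it stand in as baseline when Day 1 and Day 2 are missing, and redacted analyses cannot be checked. The other is that every subject has two readings before the first dose: a Day 2 baseline may follow it. For those subjects Screening is the only reading certain to precede treatment, which favors using it.

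Lastly, the edit touches the imputation models, the convergence fallback and several protocol paragraphs. That is a modest cost and does not defeat the proposal.

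**Conclusion.** The point holds as a missed, nearly free gain in precision. Direction and feasibility are clear: the score is pre-randomization, should be complete because eligibility depends on it, and is absent from the readable primary model. The size is not settled. The Week 12 variance reduction is about 11-22% under equal correlations of 0.5-0.9, about 2-10% under decay, and zero in the limiting autoregressive case. Power at 51 per arm goes from 80.6% to 84.5-88.5%, or to roughly 81-84%, if SD 7 is the planned model's residual SD. If SD 7 is the SD of raw change, the proportional variance reduction for given correlations is unchanged, but planned power starts higher.

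**What to change.** Before unblinding for the interim analysis, amend SAP 4.4.1 and Protocol 16.1.2.1, with matching text in the synopsis and Protocol 16.1.2.2:

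- Add the Screening value of the same endpoint and its interaction with visit as fixed covariates for MCCB Working Memory, the other MCCB scores, PANSS and CGI-S. Keep change from the Day 1 baseline as the response.
- Use the latest Screening value for a rescreened subject, and state how a subject is handled when the Screening value itself serves as baseline, since the two covariates then coincide.
- Give the new terms a place in the convergence fallback order, where SAP 4.4.1 already allows region to be dropped.
- Match the imputation models to the new covariates.
- Use the same model at the interim and final analyses.

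The cost for Working Memory is about three degrees of freedom (Weeks 2, 6 and 12) and the edits above. There is no new data collection and no added burden on subjects.

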¹ If needed, cognitive behavioral assessments may be completed over 2 consecutive working days for feasibility and subject comfort. The following efficacy assessments should, whenever possible, be completed in the following order: MCCB, [REDACTED] SCI-PANSS, UPSA-Bi, SCoRS, CGI-S, CGI-I.

² The visit window is ± 3 calendar days relative to baseline. The total time between visits is not to exceed 10 calendar days (for Week 2) or 17 calendar days (for all other visits).

³ Week 12 (Day 85/ET) assessments should be completed in the event of early subject withdrawal/early termination (ET).

⁴ The site will review all Screening Visit assessments against the inclusion/exclusion criteria, assess for any changes from screening, and reconfirm eligibility prior to randomization.

⁵ C-SSRS “Since Last Visit” evaluation.

⁶ The following safety assessments should, whenever possible, be completed in this order: C-SSRS, concomitant medications, weight, physical examination, neurological examination, SARA, 12-lead ECG, vital signs, urine drug and alcohol screening, blood/urine specimens.

⁷ See Section 8.3 and the Study Reference Manual for additional information.

⁸ All women of childbearing potential and all men must practice effective contraception during the study. After their last dose of study treatment, men and women must continue with contraception for at least 30 days.

⁹ To be performed predose for all study sites. For Japanese study sites, see Footnote 10 for additional instructions.

¹⁰ **For Japanese study sites only** (items designated with Footnote 10 are for Japanese sites only unless otherwise specified):

- On Day 1, in addition to baseline assessments, a [REDACTED] will be collected (see Table 5 for timing) and additional safety evaluations (AE recording, 12-lead ECG, brief neurological examination, and SARA) will be performed 2-hours postdose. Should any abnormal findings arise during these evaluations, an additional [REDACTED] will be collected. Dosing will be performed under medical supervision, and observation may be extended at the Investigator’s discretion prior to discharge from the site, if necessary, including an overnight stay.
- On Day 8, a [REDACTED] will be collected (see Table 5 for timing), and additional safety assessments 2-hours postdose (AE recording, 12-lead ECG, brief neurological examination, and SARA) will be performed.

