16.1.2.2. Analysis of the Secondary Endpoints

The secondary endpoints are defined in [Table 6](#). The population for the analysis will be subjects in the ITT population with a baseline and at least 1 postbaseline value. For all continuous endpoints, an MMRM model will be used to analyze change from baseline to Week 12 visit using the fixed effects of treatment, visit, treatment-by-visit interaction, baseline, baseline-by-visit interaction, and region. Sensitivity analyses based on different missing mechanism will also be performed (imputation methods are defined in the SAP).

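### The primary analysis of UPSA-Bi and SCoRS is a Week 12 complete-case ANCOVA labelled ITT; it conflicts with the protocol's population and model and ignores the interim MCCB and PANSS data.

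*SAP*

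**What the plan says.** **Protocol.** Section 16.1.2.2 says of the secondary endpoints: "The population for the analysis will be subjects in the ITT population with a baseline and at least 1 postbaseline value". It continues: "For all continuous endpoints, an MMRM model will be used to analyze change from baseline to Week 12 visit", and lists region among the fixed effects. It leaves imputation methods to the SAP. In Table 4 (Section 5) UPSA-Bi and SCoRS are scheduled at Day 1 and in the combined Week 12/ET column only, and footnote 3 asks for the Week 12 assessments when a subject leaves early. MCCB and SCI-PANSS are also taken at Weeks 2 and 6.

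**SAP, primary analysis.** Section 4.4.1 says that all efficacy analyses use the ITT population. For these two scales, however, "the primary analysis will be based on subjects who have both baseline and Week 12 assessments", and "An analysis of covariance (ANCOVA) model will be applied adjusting for treatment group and baseline value of the endpoint". Region is not in that model. For the primary analysis in general, "Data will be censored when a subject prematurely discontinues the study treatment".

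**SAP, visit mapping.** The note to Table 3, which covers these scales, says: "If subject terminate the treatment early before Day 71, their visits will be mapped to nominal visit of" early termination. That row spans Days 2 to 70; Days 71 to 91 count as Week 12. Tables 2 and 4 treat MCCB, PANSS and CGI differently: an early visit goes to an interim analysis visit according to its day.

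**SAP, labels and supporting analyses.** Table 5 (Section 4.4.3) lists this ANCOVA under ITT and per-protocol, with N/A as the missing-data assumption. The same scales also get a reference-based imputation, a complementary analysis that keeps data after treatment discontinuation, and a responder analysis that counts a missing Week 12 value as non-response.

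**The concern.** A subject who leaves on Day 50 with an ET assessment belongs to the protocol's population for UPSA-Bi and SCoRS but is absent from the SAP's primary analysis of them. The same subject's MCCB and PANSS values do enter their own repeated-measures models. So the ITT label means different things for the cognitive and the functional key secondary endpoints.

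N/A is also not an accurate entry. An ANCOVA restricted to subjects with a Week 12 value has a missing-data assumption: given arm and baseline, leaving must be unrelated to the Week 12 outcome. If subjects on active drug tend to leave when they do poorly and placebo subjects leave for other reasons, the completers flatter the drug. The trial already collects MCCB and PANSS at Weeks 2 and 6, which could weaken that assumption, and this analysis does not use them.

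**Working it through.** **1. The plan's own figures.** Inputs (protocol 16.6): difference 3.5, SD 7, two-sided alpha 0.10, power 80%, drop-out 30%.
- Normal approximation: n = 2 × (1.645 + 0.842)² × (7/3.5)² = 49.5, so 50 per arm.
- Exact t-test: 50.15, so 51 per arm, with power 80.6%.
- Inflation for drop-out: 51/0.70 = 72.9, so 73 per arm.

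The stated 51 and 73 reproduce. They were derived for MCCB Working Memory; the documents give no drop-out rate for UPSA-Bi or SCoRS.

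**2. Subjects left out by the Week 12 rule.** 0.30 × 73 = 21.9 per arm; 0.30 × 219 = 65.7 in all, leaving about 153. At 20% or 40% drop-out the total left out would be about 44 or 88.

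**3. Loss against the protocol population.** Let r be the share of drop-outs with an ET value on Days 2 to 70. The documents do not give r. The protocol population is 3 × (51.1 + 21.9r).

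| r | Protocol population | Removed by the SAP rule |
|---|---|---|
| 0 | 153 | 0 (0%) |
| 0.5 | 186 | 33 (18%) |
| 1 | 219 | 66 (30%) |

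**4. Do the supporting analyses fill the gap?**
- The reference-based imputation builds each regression from visits of the endpoint itself. With one scheduled post-baseline visit, that means baseline alone unless ET values are added. It also imputes the active arms from placebo, so it is an MNAR analysis.
- The complementary analysis prescribes the same MMRM as the primary analysis, which does not fit a single scheduled post-baseline visit. The SAP does not say how an ET value would enter.
- The responder analysis sets missing to failure.

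None gives a MAR estimate that uses MCCB and PANSS at Weeks 2 and 6.

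**5. Possible bias.** Assumptions, none of them from the documents: 30% leave each arm; in the active arm leaving depends on a normal variable with correlation 0.6 to Week 6 MCCB; placebo subjects leave at random; MCCB correlates ρ with the functional change, scored so that higher is better.
- Mean of the retention variable among the 70% retained: 0.348/0.70 = 0.497 SD.
- Bias in the treatment difference = 0.6 × 0.497 × ρ = 0.298ρ.

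| ρ | Bias (SD) |
|---|---|
| 0.1 | 0.03 |
| 0.3 | 0.09 |
| 0.4 | 0.12 |
| 0.5 | 0.15 |

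For scale, the unadjusted standard error of a difference at 51 per arm is √(2/51) = 0.20 SD. If selection is the same in both arms, the two shifts cancel.

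**The case against.** **The protocol's model would not bring anyone back.** With one scheduled post-baseline visit, an MMRM for Week 12 reduces to a complete-case ANCOVA. The SAP gives this visit schedule as its reason for the ANCOVA, and the protocol leaves imputation to the SAP. This stands: the remedy is imputation, not a return to the MMRM wording.

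**A reader might infer that 30% are dropped against the protocol.** The documents do not support that. The 30% is a planning rate for another endpoint, and drop-outs without any post-baseline value are outside the protocol population too. The loss could be smaller, because ET visits from Day 71 count as Week 12. It could be larger, because subjects who stop treatment but stay to Week 12 are censored.

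**A reader might infer that these scales are analysed in completers only, or that ET values are never used.** The restriction applies to the primary analysis. Supporting ITT analyses are planned, change is summarised at each post-baseline visit, and the complementary analysis takes all observed data. The SAP is unclear on the role of ET values there; it does not exclude them.

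**A reader might want the ET score as an imputation predictor.** That does not work. Completers have no interim UPSA-Bi or SCoRS value, and an early leaver's later Week 12 value, if any, is off treatment and censored. On-treatment ET and on-treatment Week 12 values are essentially never seen in the same subject, so their regression cannot be estimated.

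**The bias figures are constructed.** This also stands. No passage says that MCCB or PANSS predicts drop-out or functional outcome here. The nearest figure, a correlation of 0.13 to 0.27 between neurocognitive deficits and negative symptoms (protocol 4.1), concerns a different pair of variables. Subjects who leave before Day 29 have no Week 6 value, so imputation would recover less for them. The stakes are limited as well: these are Phase 2 secondary endpoints with no multiplicity-controlled claim.

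**Conclusion.** The point holds for the primary analysis of UPSA-Bi and SCoRS. It is a Week 12 complete-case analysis under an ITT label, it differs from protocol 16.1.2.2 on population, model type and region, and its missing-data assumption is not stated.

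At 30% drop-out it omits about 22 subjects per arm. Relative to the protocol population the omission lies between 0 and 30% and cannot be fixed further without the ET capture rate.

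Whether bias follows is unknown. Under one-sided selective drop-out as assumed above it is about 0.03 to 0.15 SD, always below the 0.20 SD standard error, and it is zero if drop-out is alike across arms. The documents do not show that the functional effect will be overstated. They show an avoidable reliance on a stronger assumption than the collected data require, in two named key secondary endpoints.

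**What to change.** - Make the primary analysis of UPSA-Bi and SCoRS an ANCOVA on treatment, baseline and region, after MAR multiple imputation of Week 12 within arm, for all ITT subjects with a baseline.
- Use baseline and the on-treatment MCCB and PANSS values at Weeks 2 and 6 as predictors, and name in advance which MCCB and PANSS scores these are.
- Do not use the ET value as a regression predictor; summarise ET values separately.
- Keep the completer ANCOVA as a sensitivity analysis.
- In Table 5, replace N/A with MAR for this analysis.
- Reconcile the SAP's population and model with protocol 16.1.2.2. The proposed population is wider than the protocol's, because it does not require a post-baseline value of the scale, so the change should be recorded.

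The cost is SAP wording, one more imputation program and slightly more complex output. No change to visits or data collection is needed.
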